8.2. The Number of Participants

68 full datasets (1:1 ratio intervention to control) are intended to be collected for this study. This is based on a power calculation using the between groups effect size estimate ($d=1.2$) from a previous study of digital CBT-I in people with insomnia (Espie et al., 2012). This would therefore require 24 participants in total to find an effect. However, we wish to also include people with sleep disturbance who do not meet the criteria for insomnia. Based on our open-label feasibility study for digital CBT-I in this population (Smejka et al., 2022) we anticipate that 50% of participants will not meet the criteria for insomnia, and based on that study we would anticipate a more modest effect size ($d=0.7$), which would require 68 participants (assuming $\alpha=0.05$ and power of 80%). Allowing for approximately 25% drop out, we therefore aim to recruit 86 participants in total. This should allow us to do a subgroup analysis including only people who meet the criteria for insomnia, as well as a full group analysis.

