1. SYNOPSIS

Long Study Title	An Investigation into the Efficacy of Online Cognitive Behaviour Therapy for Insomnia (“Sleepio”) for Stroke Survivors	
Short Study Title (to be used on participant-facing documents, if applicable)	Improving sleep in rehabilitation after stroke (INSPIRES)	
Nature of Study Participants	Stroke survivors	
Intended number of participants	86	
Design	Randomised controlled	
Location	In the participant's home / online	
	Objectives	Outcome Measures
Primary	The primary objective of this study is to assess whether self-reported sleep quality in stroke survivors is improved following online Cognitive Behavioural Therapy for Insomnia (“Sleepio” programme).	The primary outcome measures for this study will be the change in Sleep Condition Indicator score following completion of the programme.
Secondary	
The secondary objectives are to assess changes in measures of sleep quality and self-reported measures of quality of life and anxiety following the intervention and at 8 week follow up.
 
To assess the cost-effectiveness of online CBT-I in stroke survivors when compared to a brochure of sleep hygiene information.
	
Changes in sleep fragmentation and wake after sleep onset, assessed with actigraphy, sleep onset latency assessed through the sleep diaries, anxiety and depression using the PHQ9 and GAD7, quality of life using the Stroke impact scale-8 and Euroqol-5 Dimensions- 5 Levels (EQ-5D-5L)
 
Changes in healthcare costs during the 8-week follow up.

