4. PARTICIPANT IDENTIFICATION AND RECRUITMENT

4.1. Study Participants

68 people who have had a stroke and want to improve their sleep.

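### Recruiting 86 does not leave 68 complete datasets at 25% dropout, and section 4.1 gives 68 as the number of participants

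*Combined protocol and SAP*

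**What the plan says.** Section 8.2 states the target in completers: "68 full datasets (1:1 ratio intervention to control) are intended to be collected for this study". It derives that number from an anticipated effect: "we would anticipate a more modest effect size ($d=0.7$), which would require 68 participants", with alpha 0.05 and 80% power. It then converts completers to a recruitment target: "Allowing for approximately 25% drop out, we therefore aim to recruit 86 participants in total".

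The synopsis row headed "Intended number of participants" also gives 86. Section 4.1 describes the study participants as "68 people who have had a stroke and want to improve their sleep" and does not say that this counts completers only.

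**The concern.** Section 8.2 links three figures: 68 complete datasets, 25% dropout and 86 recruited. Any two of them fix the third, and as printed they do not agree. The inflation appears to multiply by 1 plus the dropout rate instead of dividing by 1 minus it. That error always gives too small a target.

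Section 4.1 adds a second conflict. It stands in the part of the protocol on identifying and recruiting participants, where someone would look for the number to enrol, and its figure is 18 below the other two (86 − 68). A team that took it literally would stop recruiting before the planned target and lose a good deal of power.

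**Working it through.** **Inputs**

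- Complete datasets required: 68, allocated 1:1, so 34 per arm (section 8.2)
- Effect size d = 0.7, alpha 0.05, power 80% (section 8.2)
- Dropout approximately 25%, recruitment target 86 (section 8.2)
- Intended number of participants: 86 (synopsis) and 68 (section 4.1)
- Assumed: a two-sided, unadjusted comparison of two means. Section 8.2 does not state sidedness. A one-sided test would need 25.94 per arm, so 26 per arm and 52 in total. Only the two-sided test matches the printed 68.

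**Step 1. Reproduce the plan's base figures** (two-sample t-test, two-sided alpha 0.05, 80% power)

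- d = 1.2: 11.94 per arm, rounded up to 12, so 24 in total. This matches section 8.2.
- d = 0.7: 33.02 per arm, rounded up to 34, so 68 in total. This matches section 8.2.

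The fault is therefore confined to the dropout step.

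**Step 2. Check the dropout inflation**

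- Correct formula, N / (1 − dropout): 68 / 0.75 = 90.67, so 91, or 92 for equal arms.
- Common mistake, N × (1 + dropout): 68 × 1.25 = 85, or 86 when rounded up to an even number.
- Completers from the stated target: 86 × 0.75 = 64.5, so 64 or 65, which is 3 to 4 short of 68.
- Largest dropout at which 86 still leaves 68: 1 − 68/86 = 20.9%, which is 18 of 86.

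**Step 3. Power for d = 0.7 at each number of completers**

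| Scenario | Completers | Power (t-test) |
|---|---|---|
| Target met | 68 | 81.2% |
| 86 recruited, 25% loss | 65 | 79.3% |
| 86 recruited, 25% loss | 64 | 78.7% |
| 68 recruited, 25% loss (68 × 0.75) | 51 | 68.8% |

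The effect detectable with 80% power is d = 0.69 with 68 completers, d = 0.71 with 64 and d = 0.80 with 51.

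**The case against.** The strongest reply is that this hardly matters.

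- **The allowance is approximate.** Section 8.2 does not say exactly 25%. The 68 is also slightly more than 80% power requires: 66 completers give 79.97%, and 66 of 86 corresponds to 23.3% loss (1 − 66/86). Measured against the stated 80%, the shortfall at 25% dropout is about one point. This stands as a comment on size. It does not make the figures agree, because the section sets its target as 68 full datasets and 86 delivers those only up to about 21% loss.
- **The planned analysis is more efficient than a t-test.** Section 8.1 includes the baseline score as a covariate and allows a linear mixed model. If d is standardised by the unadjusted SD, power at 64 completers would be 80.3%, 82.4% or 88.9% for an assumed baseline-to-outcome correlation of 0.2, 0.3 or 0.5. The practical loss may well be nil. However, the documents give no correlation and do not use one to justify 86.
- **The 69% figure is not the plan.** The synopsis and section 8.2 both say 86, and section 8.2 shows where 68 comes from. Section 4.1 most likely carries the completer target without its label. This is a fair point: 69% is what would follow if section 4.1 were taken literally, and the trial is not designed at that power.
- **The origin of 86 is inferred.** The protocol shows no inflation calculation, so 68 × 1.25 rounded to an even number is a likely explanation and no more. The mismatch does not depend on it.

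**Conclusion.** The point holds. The recruitment target of 86, the 25% dropout allowance and the 68 complete datasets in section 8.2 cannot all be right, and section 4.1 contradicts the synopsis and section 8.2 on the number of participants.

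The two parts differ in weight. The dropout error costs 3 to 4 completers and leaves power just under 80%, which is minor. The conflict over enrolment would matter more if section 4.1 were acted on: about 12 points of power against the 68-completer target (81.2% − 68.8% = 12.4). That reading is unlikely.

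These power figures assume a two-sided, unadjusted two-group comparison of completers at d = 0.7. Baseline adjustment would probably raise all of them, by an amount the documents do not allow to be calculated.

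**What to change.** Two wording corrections, with no change to enrolment, design or analysis:

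1. **Section 4.1:** give 86 people recruited, with 68 identified as the number of complete datasets sought.
2. **Section 8.2:** keep 86 and restate what it allows for, in one of two ways:
   - it leaves 68 complete datasets with dropout of up to about 21% (18 of 86); or
   - at 25% dropout it leaves about 64 complete datasets, giving about 79% power for d = 0.7 on an unadjusted two-sided test. In that case, also reword the opening sentence of the section and section 4.1, so that 68 appears as the number behind the power calculation and not as the expected yield.

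It would help to state in the same edit that the calculation is two-sided. The only cost is that the stated dropout allowance or the stated power becomes slightly less favourable.

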8.3. Expenses and Benefits

Postage of study materials will be covered by the research group by sending prepaid envelopes to the participants. Participants will receive a £15 shopping voucher per assessment time-point (baseline, post-intervention and 8 weeks follow up – total £45) as reimbursement for their time to complete the questionnaires/assessments. Participants in the control group will be given free access to Sleepio after the 8 week follow up.
